## **6.10 Efficacy Evaluation**

Analysis of the primary endpoint will be performed on the FAS and repeated on the PPAS.

### **6.10.1 Primary Endpoint**

The primary endpoint is the change in CRP from baseline to the mean of the last two non-missing scheduled assessments occurring during the seven day treatment period (Visits 2 to 8 and/or withdrawal). For subjects who do not complete treatment, the assessments up to and including the next-non missing assessment following the final administration of study treatment will be considered for inclusion in the mean.

The baseline CRP assessment is defined as the Visit 2 value supplied by the central laboratory where this assessment occurs prior to the first administration of study treatment. Should the Visit 2 assessment be taken after first administration of study treatment or be missing, the Visit 1 value will not be used and the baseline CRP assessment will remain missing. This avoids potential differences amongst local

laboratories that supply the Visit 1 CRP data following the protocol amendment of 14 August 2020. If necessary, the incorporation of Visit 1 local laboratory CRP values may be investigated post-hoc to support any conclusions of the CSR.

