## 6.3 Analysis Sets

The **Enrolled Set** includes all subjects who provide informed consent irrespective of whether they received the study treatment.

The **Randomised Analysis Set (RAS)** includes all subjects who have been randomised, irrespective of whether they received the study treatment.

The **Full Analysis Set (FAS)** will consist of all subjects who have been randomised and received at least one dose of IMP and who have at least one post-baseline assessment of efficacy. A post-baseline assessment of efficacy includes an assessment of any of the parameters detailed in Section 6.10 of this SAP. Subjects will be analysed according to the treatment they are assigned to at randomisation, irrespective of what treatment they actually received.

The **Per-Protocol Analysis Set (PPAS)** will be a subset of the FAS and consist of all subjects without any major protocol deviations that are judged to compromise the analysis of the data. All protocol deviations will be judged as major or minor prior to database lock.

The **Safety Analysis Set (SAS)** consists of all subjects who have received at least one dose of IMP. Subjects will be analysed according to the treatment actually taken.

The list of subjects included in the PPAS will be agreed prior to breaking the blind once all study data is available. The definitions for the enrolled set, RAS, FAS and SAS are sufficient to determine the subjects included within these analysis sets and so do not require listing and agreeing prior to breaking the blind.

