## 6.5 Disposition of Subjects

The number and percentage of all subjects enrolled, included in the RAS, FAS, PPAS and SAS, who completed study treatment and prematurely discontinued study treatment, who completed the study and prematurely discontinued the study and study duration will be summarised. The number and percentage of subjects will be summarised by their reasons for withdrawal from treatment and the study.

Study duration will be derived as the number of days between date of randomisation and the date of study completion or the date of early study withdrawal. The timing of withdrawals will be explored using the RAS. Time to withdrawal from study treatment will be calculated in hours as (Date and time of withdrawal from treatment) – (Date and time of informed consent). For subjects not withdrawing from treatment, time to withdrawal will be censored at the time of their last study treatment administration. The time to withdrawal will also be presented graphically using a Kaplan Meier (KM) plot. KM estimates for the 25th, 50th and 75th percentiles of time to withdrawal will also be presented.

Eligibility for each of the analysis sets along with reasons for exclusion will be listed. Inclusion and exclusion criteria failures will be listed. Study completion/withdrawal data will be listed.

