### Imputation

Subjects with a missing baseline assessment or no post-baseline assessment of CRP will not be imputed and will not be included in the analysis.

Post-baseline assessments up to and including the next non-missing assessment (including those at or after the withdrawal assessment) following the final treatment administration will be considered as the treatment period for inclusion in the mean. The mean of their last two non-missing scheduled assessments during the treatment period, or a single CRP value where the subject has only completed one post-baseline CRP assessment, will be carried forward to represent state at the end of trial.

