### Summaries

Descriptive statistics will summarise the CRP values and change from baseline at each assessment for each study treatment. The geometric mean, SD on the log scale and % coefficient of variation (CV) will also be presented. CRP values including the change from baseline will be listed.

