### Sensitivity Analysis

A sensitivity analysis will be conducted using the mean of the last two non-missing post-baseline values during the treatment and follow-up periods (up to and including Visit 9). If there is only one post-baseline value then this value will be used. This approach is expected to be conservative as it includes a time period when patients in the active treatment arm are potentially untreated.

The analysis will be a repeat of the ANCOVA described above.

Further sensitivity analyses may be considered post-hoc.

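### Does leaving FAS subjects without a pre-dose Visit 2 CRP out of the primary ANCOVA call for a pre-specified analysis that keeps them?

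*SAP*

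**What the plan says.** SAP 6.10 names the population: "Analysis of the primary endpoint will be performed on the FAS and repeated on the PPAS". Under SAP 6.3, entry to the FAS requires randomisation and that the subject "received at least one dose of IMP and who have at least one post-baseline assessment of efficacy". A baseline CRP is not a condition.

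SAP 6.10.1 accepts only the central laboratory's pre-dose Visit 2 value as baseline CRP. Otherwise: "Should the Visit 2 assessment be taken after first administration of study treatment or be missing, the Visit 1 value will not be used". The reason given is possible disagreement among the local laboratories that supply Visit 1 CRP after the August 2020 amendment. The Imputation paragraph gives the consequence: "Subjects with a missing baseline assessment or no post-baseline assessment of CRP will not be imputed and will not be included in the analysis".

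The one planned sensitivity analysis lengthens the post-baseline window to Visit 9 and otherwise changes nothing: "The analysis will be a repeat of the ANCOVA described above". Visit 1 values are left open: "If necessary, the incorporation of Visit 1 local laboratory CRP values may be investigated post-hoc to support any conclusions of the CSR".

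**The concern.** A subject can be randomised, dosed and sampled for CRP on treatment, be counted in the FAS, and still be absent from the analysis described as an FAS analysis. Three things make this look like a defect.

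- Every planned between-arm comparison of CRP needs the same baseline, so none brings these subjects back. Whether and how to use their Visit 1 values could be decided after unblinding.
- SAP 6.5 promises "Eligibility for each of the analysis sets along with reasons for exclusion will be listed". These subjects stay in the FAS, so that listing would not show them, and the loss might seem to go unreported.
- Protocol 6.5.2 lists the Visit 2 CRP sample and the first IMP doses without saying which comes first. A site following the protocol might therefore seem able to create an exclusion.

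At stake are precision in the primary comparison and the reader's ability to see how far the analysed group falls short of the FAS.

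**Working it through.** **1. Is any CRP comparison free of the rule?** No.

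| Planned analysis | Keeps these subjects? |
|---|---|
| Primary ANCOVA, FAS (SAP 6.10.1) | No: baseline enters both the outcome and the covariate |
| Log-transformed fallback (6.10.1) | No: same ANCOVA |
| PPAS repeat (6.3, 6.10) | No: subset of the FAS, same model |
| Visit 9 window (6.10.1) | No: same model |
| Country term, subgroups (6.10.5, 6.10.6) | No: same model |
| By-visit summaries (6.10.1) | Yes, but descriptive only |

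**2. Is the loss hidden?** No, for two reasons.

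- SAP 6.7.1 puts baseline CRP, split at the median, in the demography table, and 6.2.1 refers its definition to 6.10.1. SAP 6.4 presents that table on the FAS by arm. SAP 6.1 bases its percentages on the whole analysis set and shows missing values as a category where they occur. FAS subjects without a baseline CRP therefore appear as missing, by arm.
- SAP 6.10.1 also plans: "Descriptive statistics will summarise the CRP values and change from baseline at each assessment for each study treatment". Under 6.1 each summary carries its n. At any post-baseline visit, n for CRP minus n for change gives, by arm, the subjects with a reading but no baseline.

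**3. Does the protocol create the exclusion?** This cannot be established. Protocol 8.1.2 leaves sampling detail to the laboratory manual, which is not among the documents. In the Visit 2 list sampling stands above IMP administration, though the list is not said to be sequential. The SAP 6.2.1 rule for unclear timing at Visit 2 concerns other variables.

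**4. What could it cost?** Inputs from SAP section 3: SD of change 60 mg/L, difference 25 mg/L, two-sided 10%, 75 per arm, power about 80%.

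SE = 60 × √(2/n). At n = 75, SE = 9.798 and 25/9.798 = 2.552. Normal-approximation power = Φ(2.552 − 1.645) = 81.8%; exact noncentral t gives 81.5%. The plan's figure is reproduced. At n = 72, SE = 10.0 and exact power is 80.05%, so the design can lose 3 per arm and still reach 80%.

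The documents give no rate of missing or post-dose Visit 2 samples. Assuming equal loss in both arms:

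| Loss (assumed) | n per arm | Normal | Exact t |
|---|---|---|---|
| 0% | 75 | 81.8% | 81.5% |
| about 5% | 71 | 79.9% | 79.6% |
| about 10% | 68 | 78.4% | 78.0% |
| 20% | 60 | 73.8% | 73.4% |

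The actual analysis adjusts for baseline. Hold the SD of change at 60 and assume a baseline SD s_b and a baseline/end correlation r. Then the end SD is s_e = r·s_b + √(3600 − s_b²(1 − r²)), the baseline/change correlation is ρ = (r·s_e − s_b)/60, the residual SD is 60·√(1 − ρ²), and there are 2n − 3 degrees of freedom. For s_b = 30 and r = 0.5: s_e = 69.08, ρ = 0.076, residual SD = 59.83. Power with n = 75 × (1 − loss):

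| s_b, r (assumed) | 0% | 5% | 10% | 20% |
|---|---|---|---|---|
| 30, 0 | 90.1 | 88.7 | 87.2 | 83.5 |
| 30, 0.3 | 82.7 | 81.0 | 79.1 | 74.8 |
| 30, 0.5 | 81.7 | 79.9 | 77.9 | 73.6 |
| 30, 0.8 | 93.1 | 91.9 | 90.7 | 87.5 |

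**5. What would an analysis that keeps them gain?** In the simulation (4,000 trials per cell, baseline SD 30), missing baselines were filled from Visit 1 by a regression blind to treatment, with a missing-baseline indicator. With an assumed Visit 1/Visit 2 correlation of 0.8:

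- 5% missing: gain of 0.3 to 1.5 points.
- 10% missing: 79.0% to 82.4% (r = 0.3), 77.6% to 80.1% (r = 0.5), 89.9% to 90.9% (r = 0.8).
- 20% missing: 74.4% to 82.5% (r = 0.3), 87.4% to 90.5% (r = 0.8).

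With a Visit 1/Visit 2 correlation of 0.6 and 10% missing, the gain is 3.0 points at r = 0.3 and nil at r = 0.8. Baselines were missing at random in these runs. Mean estimates when the subjects were kept ran from −24.79 to −25.28 against a true −25. Type I error at 10% missing was 9.7 to 10.0% with the subjects excluded and 9.7 to 9.9% with them kept.

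**The case for a change.** The best argument for a change is that the sponsor foresaw the situation and left its handling optional, with no trigger and no method. Fixing one supportive model before unblinding is cheap and cannot be done afterwards. The same SAP does this elsewhere: for oxygen need, 6.10.2.2 pre-specifies a sensitivity analysis for subjects its main analysis drops. The local-laboratory reason supports the primary rule but does not explain having no planned supportive analysis.

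It stands that no planned CRP comparison keeps these subjects and that the Visit 1 method is unstated. It does not follow that the plan is unsound. The primary endpoint is a change from baseline, which does not exist without one, and the SAP openly labels any Visit 1 work as post hoc. The extra model would also have to deal with the SAP's own worry about disagreement among local laboratories, with one UK site and up to 12 in India. A term for protocol version would not separate one local laboratory from another. The simulation used a single assumed shift of +20 mg/L in a random half of subjects, so it does not test that worry.

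**Conclusion.** No change follows. The exclusion is a deliberate trade-off, stated in advance: a few subjects may be given up so that every baseline comes from one laboratory. Whether a sample was drawn before the first dose is settled at about the time of that dose, under blinding. I therefore judge the likely cost to be precision rather than bias, and nothing in the documents shows bias.

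The size is unknown because no rate of missing baselines is given. On the plan's t-test basis, a loss of about 5% costs 1.9 points of power (81.5% to 79.6%), about 10% costs 3.5, and 20% costs 8.1. Baseline adjustment may offset some or all of this, depending on a baseline SD and correlation that the documents do not give. A retained-subject model recovers little at low loss and would not alter the primary estimate. A large loss in either arm would show in the planned tables.

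The sponsor may choose to write down a Visit 1 method before unblinding and to confirm that the laboratory manual puts the Visit 2 CRP sample before the first dose. The soundness of the primary result depends on neither.

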### Primary Analysis

The null hypothesis will be that the treatments are equivalent and will be rejected in favour of the alternative hypothesis, that a treatment difference exists, should the probability of the null hypothesis being true be less than 10%.

The change in CRP from baseline to the mean of the last two non-missing scheduled assessments during the treatment period will be analysed using an analysis of covariance (ANCOVA). The model will be fitted with the change in CRP from baseline as the dependent variable and study treatment as a fixed effect. The baseline CRP value will be included as a covariate.

Adjusted Least square means (LS Means) for the treatment groups estimated by the model will be presented, together with the associated standard errors (SE) and 90% CIs. The adjusted LS Mean, SE and 90% CI and two-sided p-value of the treatment difference will also be presented.

Model assumptions will be checked. Where these assumptions are not met, data will be log-transformed and the ANCOVA will be performed on the transformed data.

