## 3 SAMPLE SIZE

Sample size is based on the assumption of a standard deviation (SD) of 60 mg/L for the change in CRP from baseline to average of last two assessments during one week of treatment. With 75 patients per group and a two-sided t-test at 10% significance level, there will be an approximative 80% power to detect a true reduction of 25 mg/L in C21 treated patients compared to placebo.

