### 6.2.4 Non-numeric Values

For clinical laboratory parameters and cytokine data, in the case where a variable is recorded as ">x", "≥x", "<x" or "≤x" rather than an exact number, then for analysis purposes a value of x will be taken. Where a range of values is quoted the midpoint of the range will be taken. Where this process is not appropriate, further information will be detailed in the relevant section. The recorded value will be reported in listings.

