#### **6.10.6 Subgroup Analyses**

The primary efficacy endpoint will be investigated using demographic and baseline value-defined subgroups as follows:

- Age ( $\leq$ median age at baseline,  $>$ median age at baseline).
- Sex (Males, Females).
- Supplemental oxygen use at baseline (Yes, No).
- CRP value at baseline ( $\leq$ median value at baseline (mg/l),  $>$ median value at baseline (mg/l)).

Each subgroup (age, sex, supplemental oxygen use and CRP) will be examined separately.

A summary table will be presented for each category of each subgroup for the primary endpoint. Analysis will be performed as described in the appropriate section for each category of the subgroup separately. Summaries and analyses will only be presented for a subgroup providing greater than 10 subjects are available for each treatment group and each category of the respective subgroup. All summaries and analyses will be presented on the FAS only.

Secondary endpoints may be explored using these subgroups and further subgroups may be also explored for all endpoints post-hoc where deemed medically appropriate following review of the data.

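### Does leaving the residual check unnamed, when it can move the primary CRP analysis from mg/L to the log scale, call for a change to the plan?

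*SAP*

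**What the plan says.** SAP section 6.10.1, Primary Analysis, defines the model: "The model will be fitted with the change in CRP from baseline as the dependent variable and study treatment as a fixed effect", with baseline CRP as covariate. The assumptions are then to be checked, and the fallback reads: "Where these assumptions are not met, data will be log-transformed and the ANCOVA will be performed on the transformed data". The SAP does not name the check, its cut-off, or when it is made relative to unblinding.

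Three other places reuse this model:

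- Section 6.10: "Analysis of the primary endpoint will be performed on the FAS and repeated on the PPAS".
- The follow-up sensitivity analysis in 6.10.1: "The analysis will be a repeat of the ANCOVA described above".
- Section 6.10.6, for subgroups: "Analysis will be performed as described in the appropriate section for each category of the subgroup separately".

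The sample size is stated in mg/L only (SAP section 3: "Sample size is based on the assumption of a standard deviation (SD) of 60 mg/L for the change in CRP"). Protocol section 13.3.1 describes the ANCOVA without a transformation. Under Summaries in 6.10.1 the SAP adds log-scale description to the mg/L summaries: "The geometric mean, SD on the log scale and % coefficient of variation (CV) will also be presented".

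**The concern.** A difference in mean change and a ratio of geometric means are different effects. If an unnamed check decides between them, two competent statisticians could follow the SAP on the same data and report different units and different p-values for the one primary test.

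Three further points made it look worse:

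- The SAP does not order a second check after logging.
- It does not say outright that the scale chosen for the FAS carries over to the PPAS, the follow-up analysis and the subgroups.
- The stated power of about 80% describes the mg/L test only.

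At stake would be the pre-specification of the primary result.

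**Working it through.** **1. The plan's own figure.** Inputs from SAP section 3: 75 per arm, difference 25 mg/L, SD 60 mg/L, two-sided 10%.

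- Standard error = 60 × √(2/75) = 9.80 mg/L, and 25 / 9.80 = 2.55.
- Normal approximation: Φ(2.552 − 1.645) = Φ(0.907) = 81.8%.
- Noncentral t with 148 df: 81.5%.

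Both agree with the stated 80% or so.

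**2. What would be logged.** A fall in CRP gives a negative change, which has no logarithm. The workable reading is therefore to log the CRP values, which gives a ratio. The geometric-mean summaries fit that reading. Results reported only as below a limit stay positive, because "then for analysis purposes a value of x will be taken" (SAP 6.2.4).

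**3. Simulation set-up.** The documents give no CRP distribution, so these inputs are assumptions:

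- Baseline uniform on 50-150 mg/L (the entry range in Protocol 5.1), correlation with end-of-treatment CRP 0 or 0.4, floor 1 mg/L.
- Sixteen lognormal or gamma settings, placebo mean 75 or 100, half with equal SDs of change and half with a proportional effect.
- Six settings mixing patients who resolve and patients who progress.
- Two near-normal settings, placebo mean 150.
- True difference about 25 mg/L, pooled SD of change 60-61, 75 per arm. There were 5,000 trials per setting for power and disagreement and 10,000 under no effect.

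A separate rerun covered 16 lognormal and gamma settings.

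**4. How often the verdict at p < 0.10 changes.**

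| Comparison | Trials with different verdicts |
|---|---|
| Always mg/L against always log, 22 skewed settings | 5-20% (median 11%) |
| Same, 16-setting rerun | 6-20% |
| Three checks: Shapiro-Wilk p < 0.05, skewness over 1, skewness over 2 (absolute values) | 1-15% (median 7.5%) |
| Shapiro-Wilk against skewness over 1 | 0-9% |
| Same, 16-setting rerun | 0-4% |
| Choice of check, two near-normal settings | 0.4-2% |

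The first two rows compare fixed scales, a choice the SAP does not offer. The gap is the unnamed check, so the lower rows measure it. Most of the three-check figure comes from the threshold of 2, which tolerates marked skew and was picked for the simulation. In the skewed settings Shapiro-Wilk fired in 93-100% of trials, so an analyst using it would nearly always reach the same scale.

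**5. Type I error under no effect.**

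| Rule | Rejection rate (nominal 10%) |
|---|---|
| mg/L throughout | 9.2-10.4% |
| Log ratio throughout | 9.5-10.7% |
| Each of four fixed rules, applied to unblinded residuals | 7.7-10.8% |
| Picking whichever p-value is significant | 12.6-15.2% |

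Only the last row inflates error materially, and the SAP does not permit it: the scale follows the assumptions, not the p-value.

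**6. The steps said to be undecided.** After a failed check the SAP orders the ANCOVA on transformed data and stops there, so the log result stands. For the PPAS and the follow-up analysis it asks for a repeat, and a repeat naturally keeps the model and scale already chosen. Only the subgroup sentence is open. Read as a fresh check in each half of the median split on baseline CRP, it put the halves on different scales in 0-49% of trials (Shapiro-Wilk) or 7-73% (skewness over 1). Those analyses are not the primary test.

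**7. What fixing mg/L would do to power.** Across the 22 skewed settings, power was 81-91% on mg/L and 70-99.9% on log. Switching on Shapiro-Wilk moved power from 14 points below the mg/L test to 18 points above it. In the rerun, log had more power in 12 of 16 settings (by about 4-20 points) and less in 4 (by about 5-14 points).

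**The case for a change.** The strongest case is that checking assumptions is ordinary, but leaving the primary effect measure to an unnamed check is not full pre-specification. Nor is the switch needed for validity, since mg/L ANCOVA held its level under skew. The three checks together chose different scales in 28-99% of skewed trials. After logging, residuals still failed Shapiro-Wilk in 72-95% of switched gamma trials and 71-99% of mixture trials (4-9% for lognormal), so a one-step rule may end on a scale that does not fit either. SAP section 6.12 does not list the fallback among changes from the protocol.

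Part of this stands. The diagnostic, its threshold and its timing are not written down, and neither is a common scale for subgroup categories. A mg/L difference and a ratio are different effects, and the 80% power belongs to the first.

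The rest carries less weight. Choosing a different scale matters to the decision only when the verdict changes, which is much rarer. Failing a normality test after logging did not spoil the test, which kept 9.5-10.7% under no effect. Protocol section 13 leaves technical detail to the SAP, and a fallback is such detail. The unit of the reported effect shows which scale was used, and descriptive summaries on both scales are already planned.

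**Conclusion.** No change follows. The SAP gives a primary model, a fallback and the order in which they apply. What it omits is the kind of detail a trial statistician supplies as a matter of course. Filled in with either of two ordinary checks, the gap alters the verdict in 0-9% of skewed trials at the planned effect (0-4% in the rerun) and hardly at all in near-normal data. Type I error stays near or below 10% under every fixed rule tried, even with the check made on unblinded residuals.

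Making mg/L the only primary scale would remove the ambiguity. It would also give up as much as 18 points of power in some settings while avoiding a loss of as much as 14 in others. Reasonable statisticians would differ on that in a proof-of-concept phase 2 trial tested at 10%, so it is a choice and not a correction.

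The conclusion rests on assumed CRP distributions. The simulated baseline was confined to the entry range, whereas the analysis baseline is the Visit 2 central-laboratory value, which need not lie within it. Country was not simulated. The conclusion also assumes that the scale is chosen from the residuals and not from the p-values, as the SAP says.
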